Objectives: To evaluate the impact of LSQ on (1) participation in physical therapy using Pittsburg Rehabilitation Participation Scale; (2) quality of life using Quality of Life – Alzheimer’s Disease Scale (participant’s version); and (3) depression symptoms using Cornell Scale for Depression in Dementia (CSDD).

Methods: A consecutive sample of convenience of up to 60 patients with mild to moderate cognitive impairment with 44 (22 per group) completing the study will be recruited from a nursing home facility. Patients will be randomly allocated in two groups: (1) *Control group*, which will receive standard physical therapy care without LSQ use; and (2) *Experimental group*, where physical therapists will use the LSQ. Each patient’s family member will receive a LSQ to complete prior to the start of the intervention. Patients’ participation, quality of life and depression symptoms will be measured on day 1 and again after 3 weeks (mid-term), and 6 weeks of intervention. Quality of life and depression symptoms will also be measured 6 weeks following intervention. A licensed occupational therapist blinded to the participants’ group allocation will measure all three dependent variables

Statistical Analysis: Descriptive statistics including means, standard deviations, frequency counts, median, mode, variance and frequency counts will be used to assess sample demographics. The Rank Sum test will be used to assess differences in Pittsburg Rehabilitation Participation Scale between the intervention and control group. Spearman Rank correlations will be used to determine the strength of the correlation between Mini-Mental state examination, Pittsburg Rehabilitation Participation Scale and Quality of Life Alzheimer Disease.

Key words: Dementia, Life story questionnaire, Physical therapy, Participation, exercise

Financial Disclosure and Conflict of Interest: The investigators affirm that they have no financial affiliation (including research funding) or involvement with any

commercial organization that has a direct financial interest in any matter included in this manuscript.

NON-SCIENTIFIC ABSTRACT

Background: Dementia is a general term for difficulties remembering, thinking or making decisions. Dementia increases among people aged 65 years or older. Exercise benefits dementia patients, however participation in activities is very difficult due to difficulties communicating and understanding. Several studies demonstrated that life story books usage improved quality of life, depression symptoms, moods and participation in activity in people with dementia. However, these studies did not evaluate the effect of Life Story Questionnaire (LSQ)– a type of life story book - on physical therapy participation, depression symptoms, and quality of life.

Objectives: To see the benefits of LSQ on (1) participation in physical therapy; (2) depression symptoms; and (3) quality of life.

Methods: Up to 60 patients with mild to moderate cognitive impairment with 44 (22 per group) completing the study will be recruited from a nursing home facility. Patients will be allocated in two groups: (1) *Control group*, which will receive standard physical therapy care without LSQ use; and (2) *Experimental group*, where physical therapists will use the LSQ. Each patient's family member will receive a LSQ to complete prior to the start of the intervention. Patients' participation, quality of life and depression symptoms will be measured on day 1 and again after 3 weeks (mid-term), and 6 weeks of intervention. Quality of life and depression symptoms will also be measured 6 weeks following intervention. An occupational therapist will take the measurements.

Statistical Analysis: Appropriate statistics will be used to analyze the data.

LIST OF ABBREVIATIONS

Cornell Scale for Depression in Dementia.....	CSDD
Life story books.....	LSBs
Life Story Questionnaire.....	LSQ
Mini-Mental State Examination.....	MMSE
Quality Of Life – Alzheimer’s Disease Scale.....	QOL-AD

BACKGROUND

Dementia is a devastating disease that places a significant physical, emotional and financial burden on patients, their caregivers and society¹. In 2015, the number of people living with dementia worldwide was estimated at 46.8 million. This number is expected to increase to 74.7 million in 2030 and 131.5 million in 2050². In the US alone, dementia was responsible for a total expense of US\$277 billion in 2018, and is expected to reach approximately US\$1.1 trillion in 2050³.

Dementia is a medical condition in which there is a worsening in a person's cognitive abilities compared with several months or years before. A person with dementia has difficulty with several types of cognitive abilities, most often with memory but also with language, attention, orientation, judgment, and planning⁴. Communication is a major concern for people with dementia^{5,6}. Positive, person-centered communication is important to ensure good quality dementia care^{6,7,8}. In 2016, the American Geriatrics Society Expert Panel developed a summarizing definition of person-centered care: "Person-centered care" means that individuals' values and preferences are elicited and, once expressed, guide all aspects of their health care, supporting their realistic health and life goals. Person-centered care is achieved through a dynamic relationship among individuals, others who are important to them, and all relevant providers. This collaboration informs decision-making to the extent that the individual desires^{2,9}. It can be enhanced by using reminiscence therapy¹⁰.

Life story book (LSB) is a common approach in reminiscence therapy¹¹. Life story books involve events and experience from the past, which can evoke memories, stimulate mental activity and improve well-being¹². Several studies demonstrated that life story books usage improved quality of life, depression and participation in activity in people with dementia in nursing homes¹²⁻¹⁴. Life story books demonstrated positive effects on communication and interaction of persons with dementia immediately after the end of treatment, and also weeks to months later¹². The majority of the life story books were tangible books, although some digital applications exist¹⁵. Qualitative findings demonstrated the value of life story books in triggering memories and in improving the relation with persons with dementia. Learning personal features and life events about dementia residents is beneficial to know actual facts as everything they state is not necessarily true¹⁴. Engaging in life story work, enabled staff to appreciate the person behind the dementia. Understanding (as opposed to knowing) the person with dementia's life story changed staff's thinking on what was important when delivering care to people with dementia².

The Crisis Prevention Institute developed a Life Story Questionnaire (LSQ) (Appendix A), which is a type of life story book for people with dementia. The information about LSQ can be gathered from multiple sources, especially family members. It includes information about preferences and lifestyle. Preferences include coffee vs tea, nickname vs full name, early riser vs night owl, small groups vs large groups, brands of personal care products. Lifestyle examples include culture, faith, family, relationships, job history, home, childhood

home and neighborhood, accomplishments, daily routine, and emotional needs. Understanding patient's preferences, values, and motivation in life is the foundation of person-centered dementia care.

The LSQ allows caregivers to start conversations about topics that are important to each patient, can help establish rapport between caregiver and patient. Clinicians' LSQ knowledge for each patient gives dementia patients security because even when they do not remember life facts, clinicians can still provide relevance to patients, creating a sense of familiarity and personhood. Additionally, the LSQ helps reduce psycho-social behaviors such as anger, agitation and depression when caregivers thoroughly understand patients' likes, dislikes, preferences, interests, and background. The LSQ can be used as a person's identity keeper¹³.

Older people have low levels of physical activity and even lower for people with dementia⁷. Physical activity is a potentially modifiable risk factor to reduce the risk of developing dementia as it can provide beneficial effects on brain health and cognition⁷. Regular exercise can positively impact dementia related symptoms including depression, anxiety, attention-deficit/hyperactivity disorder¹⁶. Additionally, it can relieve stress, improve memory, help sleep quality, and boost overall mood¹⁶. In older dementia adults living in residential care facilities, physical exercise helped patients improve their balance and maintain their independence¹⁷. However, participation in physical therapy for people with dementia is exceedingly difficult due to cognitive impairments. Physical therapists may need to develop other strategies to ensure that people with dementia

receive the input they need, such as improving caregivers' involvement or incorporating exercises into more functional activities that can be undertaken with less supervision, while promoting self-efficacy¹⁸.

Cognitive impairment is the clinical hallmark of dementia; however noncognitive neuropsychiatric symptoms are exceedingly common and dominate the presentation. Neuropsychiatric symptoms such as depression, psychosis, agitation, aggression, apathy, sleep disturbances, and disinhibition are common in people with dementia¹⁹. Non-pharmacologic techniques have substantial scientific evidence but are currently under-utilized in standard care. Kale et al. developed the Describe, Investigate, Create and Evaluate (DICE) approach, which is patient and caregiver centered and has demonstrated better outcome than pharmacological approach with less adverse effects¹⁹.

Dementia and the related neuropsychiatric symptoms affect the quality of life of dementia individuals. Dementia causes a decrease in cognitive function, so quality of life has historically been reported by proxies such as family members or health-care providers²¹. Reminiscence activities/life story book can contribute to cognitive functioning, depression, and quality of life of persons with dementia^{2,12}.

Elfrink et al. researched LSBs/LSQ interventions for people with dementia and confirmed the use of LSBs is promising to support reminiscence and personcentered care. The authors showed that creating and implementing LSBs/LSQ in dementia care seemed beneficial, although their effectiveness and long-term effects have not been investigated².

Dementia - Life Story Questionnaire – Physical Therapy

Therefore, the purpose of this study will be to evaluate the impact of LSQ use on (1) cognitively impaired patients' physical therapy activity participation; (2) quality of life; and (3) depression symptoms.

PURPOSE, AIMS AND VALUES

Purpose: The purpose of this study is to evaluate in patients with cognitive impairment the impact of LSQ on (1) physical therapy participation; (2) quality of life; and (3) depression symptoms.

Aims: The study plans to evaluate the impact of LSQ use on participation in physical therapy, quality of life and depression symptoms in people with cognitive impairment. The intervention will include gathering LSQ information for selected subjects from family patient/family members and then using this information for 6 weeks to evaluate the impact of LSQ on (1) participation in physical therapy using the Pittsburg Rehabilitation Participation Scale (Appendix B); (2) quality of life using the Quality of Life – Alzheimer’s Disease Scale (participant’s version) (Appendix C); and (3) depression symptoms using the Cornell Scale for Depression in Dementia (CSDD) (Appendix D).

Value: Previous studies demonstrated psychosocial life story book usage benefitted people with dementia in nursing homes, their relatives, and staff¹²⁻¹⁴. As per Woods et al. the life story book is beneficial to improve cognitive function, communication, quality of life and mood. However, randomized comparison trials are needed to evaluate the effect of life story book usage on physical therapy participation. People with dementia demonstrate challenges in physical therapy participation due to poor cognition and communication. Physical therapists are challenged to develop plans of care for people with dementia due to poor cognition. The LSQ can help develop individualized and person-centered care. It is hypothesized that the LSQ will help increase physical therapy participation for

Dementia - Life Story Questionnaire – Physical Therapy

people with cognitive impairment and therefore improve their functional mobility, activities of daily living, depression symptoms and quality of life. If LSQ proposed benefits are substantiated, this study could be the first to highlight the importance of LSQ increasing physical therapy participation and improving depression symptoms and quality of life in patients with cognitive impairment.

RESEARCH QUESTIONS, HYPOTHESES AND VARIABLES

RESEARCH QUESTION(s) (RQs)-This project aims to answer the following research questions:

1. **RQ 1:** What is the effect of LSQ usage on physical therapy participation in people with cognitive impairment at 3 weeks(mid-term) and six weeks as compared to a control group?
2. **RQ 2:** What is the effect of LSQ usage on quality of life in people with cognitive impairment at 3 weeks(mid-term), six weeks and six weeks following intervention as compared to a control group?
3. **RQ 3:** What is the effect of LSQ usage on depression in people with cognitive impairment at 3 weeks(mid-term), six weeks and six weeks following intervention as compared to a control group?
4. **RQ 4:** What is the relationship between cognitive impairment severity and physical therapy participation improvement at the end of the intervention (6 weeks)?

RESEARCH HYPOTHESES -This student has devised the following research experimental hypotheses

1. **Research Hypothesis 1:** LSQ usage will increase physical therapy participation in people with cognitive impairment at 3 weeks(mid-term) and six weeks as compared to a control group.

2. **Research Hypothesis 2:** LSQ usage will improve symptoms of depression in people with cognitive impairment at 3 weeks(mid-term), six weeks and six weeks following intervention as compared to a control group
3. **Research Hypothesis 3:** LSQ usage will improve quality of life in people with cognitive impairment at 3 weeks(mid-term), six weeks and six weeks following intervention as compared to a control group.
4. **Research Hypothesis 4:** Mild cognitive impairment will be positively associated with participation in physical therapy at six weeks following LSQ usage as compared to a control group.

COMPARISON VARIABLES

Independent Variable(s)-The student plans to use the following Independent Variable(s) (IV)

1. IV1: physical therapist use of LSQ
 - a. Level 1: LSQ usage
 - b. Level 2: no LSQ usage

Dependent Variable(s)-The Student plans to measure the following dependent variable(s) (DV)

1. DV1: Pittsburg Rehabilitation Participation Scale²⁵(Appendix B)
2. DV2: Quality of Life (quality of life - Alzheimer's disease scale - participant's version)²⁶(Appendix C)

3. DV3: Depression (Cornell Scale for Depression in Dementia (CSDD)²⁷(Appendix D)

Relationship Variable(s)- The investigator plans to use the following variables (RV) for RQ 4

1. RV1: Pittsburg Rehabilitation Participation Scale²⁵(Appendix B)
2. RV2: Mini-mental state of examination (MMSE)^{22,23} = Measure of dementia severity³ (Appendix E)

METHODS

Research Design

Prospective Randomized Control Trial. The trial will be registered on Clinicaltrials.gov.

Research Setting/Location

Peachtree Place (Dementia care facility), Weatherford, Texas. This study will be approved by Texas Tech University (TTU) Institutional Review Board (Lubbock Campus).

Power Analysis

Power calculations were performed to determine the sample size required for the study using the Pittsburgh participation in rehabilitation scale as the primary outcome measure and calculations using Mann-Whitney U test. The study was designed with α value set at 0.05 and Power set at 0.8 (β set at 0.2). The effect size was calculated using G*Power (version 3.1) using differences in the Pittsburgh participation in rehabilitation scale between the experimental versus the control group of 0.5 with a standard deviation of 0.5, based on pilot testing conducted at Peachtree Place, which resulted in effect size of 1 and a sample size of 44 (22 participants in each group) (<http://www.gpower.hhu.de/>).

Sampling

A consecutive sample of convenience of up to 60 patients (44 patients = 22 per group completing the study) with MMSE scale score between 10-18 (moderate cognitive impairment) and 19-23 (mild cognitive impairment), and residing at the Peachtree Place dementia care facility in Weatherford Texas will

be recruited. Patients (or their families) will be asked to participate after explanation of the study.

Subjects

Inclusion Criteria: (1) Patients residing in Peachtree Place in Weatherford, Texas; (2) Age 60-89 years; (2) Diagnosis of dementia disease, in mild to moderate stage using the MMSE (score between 10-23)^{22,23} and (3) attendance to physical therapy for 6 weeks.

Exclusion Criteria: (1) Unable to speak English; (2) blindness; (3) deafness; (4) MMSE score >23 and (5) history of major psychiatric disorder such as schizophrenia and bipolar disorder that required hospital admission within the last year.

Sequence

Reliability Testing

Investigator 2, who is a licensed occupational therapist with 15 years of clinical experience in geriatric population care, will be educated to collect the three dependent variables including the Pittsburg Rehabilitation Participation scale, the quality of life -Alzheimer's disease scale and the Cornell Scale of Depression in Dementia (CSDD) scale to establish intra-rater reliability.

Investigator 1 who is the principal investigator and a licensed physical therapist with 10-year experience treating geriatric population and has experience in using the Pittsburg Rehabilitation Participation scale, the quality of life -Alzheimer's disease scale and the CSDD scale, will explain and educate Investigator 2 in

each scale usage. After demonstration, Investigator 2 will record the three dependent variables measurements on the same patients twice, with at least 48hour interval between measurements. A minimum of five patients will be used. The intra-rater reliability of measurements on the two separate days will be calculated.

Study Sequence

Investigator 1 will conduct patients' screening (Appendix F) before they enroll the study to determine their eligibility. Participants with mild cognitive impairment (MMSE 19-23) demonstrating understanding of the research and the consent decision and indicating a willingness to take part will be asked to sign a consent form. For participants with moderate cognitive impairment (MMSE 10-18), both the potential participants and their legally authorized representatives will be asked to give consent to allow study participation.

Patients will be randomly assigned using block randomization with a 1:1 allocation ratio and randomly permuted block sizes of 2 to 6 based on severity of cognitive impairment. The randomization will be performed in R software (version 4.1.2, R Core Team) using the randomize R package (version 2.0). Each subject will be randomized to one of two interventions: (1) Control group, which will receive standard physical therapy care without LSQ use; and (2) Experimental group, where physical therapists will use the LSQ. The randomization file will be generated by Investigator 1 (Physical therapist) not involved in the data collection process, with the results stored in a spreadsheet accessible only to the investigator responsible for the subjects' group assignment. This investigator will

not participate in any data collection. Due to the nature of the study, participants will not be blinded to the group assignment and to the treatment they will receive. Investigator 2 measuring the dependent variables, however, will be blinded to the group assignment.

Family members of each patient will receive an LSQ to complete prior to the start of the intervention (Appendix A). Investigator 1 will conduct all physical therapy sessions for the study patients. Investigator 2, will collect the following dependent variables on day 1 of week 1, and on day 1 of third and sixth weeks:(1) Pittsburg Rehabilitation Participation Scale, which measures patients' participation in therapy; (2) Quality of Life - Alzheimer's disease scale; and (3) depression symptoms (Cornell Scale for Depression in Dementia). Additionally, Investigator 2 will record quality of life and depression at six-week following the intervention. Both investigators will enter their data using Texas Tech University Health Sciences Center password protected Qualtrics platform.

Both control and intervention groups will receive individual exercises that include strengthening, balance, gait, aerobic, endurance, dual cognitive motor tasks and exercises to improve activities of daily living and functional mobility²⁸. A pragmatic exercise program will be used for each participant needs based on physical therapy evaluation and goals. Each session will last approximately 60 minutes with five minutes warm up and five minutes cool down, three to five times per week for six weeks.

All patients will be charged for physical therapy services provided, as these services are standard of care, but there will be no charge for the LSQ use.

Upon completion of the trial, if LSQ results in outcomes improvements, the control group will receive six weeks of physical therapy using LSQ. All licensed therapists who participate in this research completed the Collaborative Institutional Training Initiative (CITI) training.

Example of LSQ usage: [name] has been diagnosed with dementia and scores 15 (Mild Cognitive Impairment) on MMSE scale. His family has completed LSQ and submitted it to the facility. All Peach Tree Place employees have access to LSQ to facilitate patient care. Patient's LSQ mentioned that patient loves coffee, enjoys playing cards and likes everything about cars. This patient is always excited to come to therapy when physical and occupational therapists (clinicians) mention drinking coffee together. Once patient arrives in therapy room, the clinician plays different card games with this patient in standing, to improve standing tolerance, also use balance board to challenge standing balance and to facilitate functional mobility. The clinician talks about cars, shows variety of car magazines while working on leg exercises. So, this clinician used various information from LSQ for this patient to motivate and improve therapy participation.

Outcome Assessment:

1. Pittsburgh rehabilitation participation scale (Appendix B) – to measure participant's participation in physical therapy
2. Quality of life in Alzheimer's disease – participant's version (Appendix C) – to access quality of life in dementia participants

3. Cornell scale for depression in dementia (Appendix D) – to access depression symptoms in dementia participants

Data Analysis

Descriptive statistics (means, medians, modes, standard deviations, frequency counts, minimum and maximum values) will be calculated using Excel version 2017 and SPSS version 20 (IBM Corp. Released 2011. IBM SPSS Statistics for Windows, Version 20.0. Armonk, NY: IBM Corp.) for the subjects' characteristics including age, gender, marital status, education, severity of cognitive impairment (MMSE) and living with family prior to admission to the dementia facility and the dependent and relationship variables.

Inferential statistics: the following statistics will be calculated using Jamovi version 1.6.

Research Questions 1-3: Because the data are ordinal (Pittsburg Rehabilitation Participation Scale, Quality of Life Alzheimer Disease, CSDD), the Mann-Whitney U test will be used to assess differences between the intervention and control group.

Research Question 4: Because the data are ordinal (MMSE, Pittsburg Rehabilitation Participation Scale) Spearman Rank correlations will be used to determine the strength of the correlation between MMSE and Pittsburg Rehabilitation Participation Scale.

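### The printed power inputs give 36 to 40 completers, not 44, and the primary participation scale has no named deciding visit, no success rule and two conflicting visit schedules

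*Combined protocol and SAP*

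**What the plan says.** **Sizing (Methods, Power Analysis and Sampling).** The Pittsburgh participation scale is the primary outcome and the test is Mann-Whitney U. Alpha is 0.05, with "Power set at 0.8". A pilot difference of 0.5 and SD of 0.5 were entered in G*Power, "which resulted in effect size of 1 and a sample size of 44 (22 participants in each group"). Sidedness, parent distribution and visit are not given. Sampling makes clear that the 44 are completers out of up to 60 recruited: "44 patients = 22 per group completing the study".

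**Visits compared.** Research Question 1 asks "What is the effect of LSQ usage on physical therapy participation in people with cognitive impairment at 3 weeks(mid-term) and six weeks", and Hypothesis 1 says "LSQ usage will increase physical therapy participation in people with cognitive impairment at 3 weeks(mid-term) and six weeks", each against control.

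**Analysis (Data Analysis).** For Research Questions 1 to 3, "the Mann-Whitney U test will be used to assess differences between the intervention and control group". Alpha is .05 for every analysis. No visit is named and there is no rule for combining visits.

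**Timing.** In the Abstract (Methods), outcomes are "measured on day 1 and again after 3 weeks (mid-term), and 6 weeks of intervention". In Study Sequence they are collected "on day 1 of week 1, and on day 1 of third and sixth weeks". The Appendix B form has a fourth participation row, six weeks after the intervention ends. The Abstract, Research Question 1 and Study Sequence do not include that rating.

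**The concern.** There are two linked problems.

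1. **The sample size does not follow from its printed inputs.** On its own this is minor, and it errs on the safe side under the plan's own method. But different unstated settings lead to 44, and they imply different designs: more power, a smaller alpha, or a smaller effect. A reader cannot tell which one the trial has.

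2. **The primary analysis is not fully defined.** One comparison was sized, but two visits fall under the primary hypothesis. If a significant result at either visit would count, the false-positive chance on the primary scale exceeds 5%. If both are needed it does not, but power is lower than for a single test. The schedule conflict adds to this: a six-week rating could fall at the end of the programme or about a week before it. Study Sequence also makes a post-trial step for the control group depend on whether outcomes improve, without defining improvement.

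**Working it through.** **Inputs.** From Power Analysis: d = 0.5/0.5 = 1, alpha 0.05, power 0.80. From Study Sequence: 1:1 allocation. Sidedness and parent distribution are unstated, so each was tried.

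**Method.** Mann-Whitney power by the asymptotic relative efficiency (ARE) approach. With n per group, set m = n × ARE, df = 2m − 2 and noncentrality = d × √(m/2), and take power from the noncentral t. ARE is 3/π = 0.955 for a normal parent and 0.864 for the minimum.

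**Attempt to reproduce 44, two-sided 0.05**

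| Parent | n per group | m | df | Noncentrality | Power |
|---|---|---|---|---|---|
| Normal | 17 | 16.23 | 30.47 | 2.849 | 0.788 |
| Normal | 18 | 17.19 | 32.38 | 2.932 | 0.812 |
| Minimum ARE | 19 | 16.42 | 30.83 | 2.865 | 0.792 |
| Minimum ARE | 20 | 17.28 | 32.56 | 2.939 | 0.814 |
| Normal | 22 | 21.01 | 40.02 | 3.241 | 0.885 |
| Minimum ARE | 22 | 19.01 | 36.02 | 3.083 | 0.851 |

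The totals are 2 × 18 = 36 and 2 × 20 = 40. One-sided, they are 28 and 32. Logistic and Laplace parents give 32 and 24 two-sided, 24 and 18 one-sided. None gives 44. Dropout is no explanation, because the 44 are completers.

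**Settings that do give 22 per group**

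- Power 0.85, minimum ARE, two-sided 0.05: 21 gives 0.833, 22 gives 0.851.
- Power 0.80, normal parent, two-sided 0.025 (0.05 split over two visits): 21 gives 0.794, 22 gives 0.815.
- Power 0.80, two-sided 0.05, d slightly below 1: 0.934 to 0.957 with minimum ARE (SD 0.522 to 0.535 at difference 0.5), or 0.886 to 0.908 with a normal parent.

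**Whole-number ratings.** Appendix B records one integer from 1 to 6, so ties matter. In simulations of the tie-corrected test with 22 per group at 0.05, power is about 0.87 to 0.91 if 0.5 is the SD of recorded ratings. If 0.5 is instead an SD before rounding (an assumption), the recorded SD is about 0.57 to 0.58 and power about 0.79; 23 per group gives 0.81.

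**Two visits, each tested two-sided at 0.05.** Bivariate normal test statistics; the correlation r is an assumption. Both = 2 × 0.05 − either; for example, at r = 0.5, 0.100 − 0.091 = 0.009.

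| r | False positive, either | False positive, both | Power for both, normal | Power for both, minimum ARE |
|---|---|---|---|---|
| 0.5 | 0.091 | 0.009 | 0.810 | 0.759 |
| 0.7 | 0.083 | 0.017 | 0.826 | 0.780 |
| 0.9 | 0.070 | 0.030 | 0.851 | 0.810 |

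Testing each visit at 0.025 gives per-visit power of 0.815 (normal) or 0.768 (minimum ARE) at 22 per group. Under minimum ARE, 24 per group gives 0.809.

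**Timing.** Day 1 of week 3 follows two completed weeks and day 1 of week 6 follows five. The Abstract says after three and after six. Research Question 4 treats six weeks as the end of the intervention, which agrees with the Abstract and not with Study Sequence.

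**The case against.** - **Rounding.** The pilot figures are given to one decimal. A difference and SD each between 0.45 and 0.55 allow d from 0.45/0.55 = 0.82 to 0.55/0.45 = 1.22, and both d windows that yield 22 per group lie inside that range. A difference of 0.50 with SD 0.53 gives d = 0.94 and would print as stated. This stands as a possible explanation, so the exact claim is that 44 cannot be reproduced from the figures as printed. Nothing in the plan shows that rounding is the cause.
- **The gap is harmless.** It is conservative on the continuous-data method, and alone it would be a reporting note. That is accepted.
- **The low-power scenario is strained.** A pilot SD is most naturally the SD of recorded ratings, which gives 0.87 to 0.91. That is fair; the pre-rounding case is a sensitivity check that the sponsor can settle from the pilot data.
- **Inflation is not shown.** Per-visit testing is inferred from Research Question 1 and the common alpha, the plan never states an either-visit rule, and Hypothesis 1 can be read as requiring both visits. This also stands. The fault is that the rule is missing, not that error is demonstrably inflated.
- **The timing can be inferred.** Research Question 4 and the mid-term label at three weeks support the Abstract. They narrow the conflict, but Study Sequence still gives a different schedule. The extra Appendix B row is only a form detail.

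**Conclusion.** The concern holds and should be fixed. The printed inputs give 36 to 40 completers two-sided, and 44 corresponds to 85% to 89% power for one test on the continuous-data method. The trial is not shown to be too small; its sample size is not traceable.

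The missing primary visit and success rule, with the schedule conflict, are the main reason to act. At assumed correlations of 0.5 to 0.9, the false-positive chance on the primary scale is about 7% to 9% under an either-visit rule and 1% to 3% if both are required. Requiring both gives power of 0.81 to 0.85 (normal) or 0.76 to 0.81 (minimum ARE) at 44 completers. The plan does not say which of these designs it is.

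**What to change.** 1. **Sizing.** State the sidedness, the parent distribution, the unrounded pilot difference and SD, and whether 0.5 is the SD of recorded ratings. Then correct the input actually used, or restate the size as 36 to 40 for 80% power, or state 85% to 89% power at 44, noting that this ignores ties.
2. **Schedule.** Reconcile Study Sequence with the Abstract so that each participation rating is defined in completed weeks of intervention. Remove the fourth Appendix B row or state its role.
3. **Decision rule.** Name one primary participation visit at 0.05 and label the other secondary. The end-of-intervention assessment is a reasonable choice, but it is the sponsor's to make. Alternatively, require both visits, or test each at 0.025, and state the power at 44 completers.

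**Cost.** Correcting the sizing text, reconciling the schedule and naming one visit need wording only and no patients. The price is that a result at the other visit alone could no longer be claimed as primary. If both visits stay primary, 44 completers suffice under a normal parent. Under minimum ARE, testing each at 0.025 has per-visit power 0.77 and needs 24 per group for 0.81. In the less likely case of a pre-rounding SD, simulated power is 0.66 to 0.71 if both are required and 0.69 per visit at 0.025, where 28 per group would give 0.81.
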